Appendix 2 Dosing Schedule

[figure not shown]
		PERIOD 1								PERIOD 2					
GROUP 1	Day(s) Bexagliflozin tablet, 20 mg Digoxin, 0.5 mg	Treatment A								Treatment B					
		1	2	3	4	5	6	7	8	19	20	21	22	23	24
		X	X	X	X	X	X	X	X						
				X						X					
GROUP 2	Day(s) Bexagliflozin tablet, 20 mg Digoxin, 0.5 mg	Treatment B						Treatment A							
		1	2	3	4	5	6	15	16	17	18	19	20	21	22
								X	X	X	X	X	X	X	X
		X								X					

[figure not shown]

AUC	area under the plasma concentration-time curve
AUC _{extr}	extrapolated area under the plasma concentration-time curve
AUC _{0-∞}	area under the plasma concentration-time curve from Time 0 to infinity
AUC _{0-t}	area under the plasma concentration-time curve from Time 0 to Time t
BLOQ	below the limit of quantitation
BMI	body mass index
BP	blood pressure
BUN	blood urea nitrogen
Ca	calcium
Cl	chloride
C _{last}	concentration corresponding to T _{last}
CL/F	apparent oral clearance
cm	centimeter
C _{max}	maximum observed plasma concentration
CRF	case report form
CV	coefficient of variation
DBP	diastolic blood pressure
DDI	drug-drug interaction
dL	deciliter
DM	data management

Abbreviation	Term
ECG	electrocardiogram
FDA	Food and Drug Administration
FPG	fasting plasma glucose
h	hour(s)
HBsAg	hepatitis B surface antigen
HCO ₃	Bicarbonate
Hct	hematocrit
HCV	hepatitis C virus
HDL-C	high density lipoprotein cholesterol
Hgb	hemoglobin
ICF	informed consent form
IRAE	immediately reportable adverse event
K	potassium
kg	kilogram
KR	Kenward-Roger
L	liter
λ_z	terminal elimination phase rate constant
LDL-C	low density lipoprotein cholesterol
LLN	lower limit of normal
LS	least square
MCH	mean corpuscular hemoglobin
MCHC	mean corpuscular hemoglobin concentration
MCV	mean corpuscular volume
MedDRA	Medical Dictionary for Regulatory Activities
mg	milligram
min	minute

Abbreviation	Term
mL	milliliter
msec	millisecond
Na	sodium
NCA	non compartmental analysis
NTR	not treatment related, includes unrelated
OHA	oral hypoglycemic agent
OTC	over the counter
PCS	potentially clinically significant
PE	physical examination
PK	pharmacokinetic
PR	The period that extends from the beginning of the P wave (the onset of atrial depolarization) until the beginning of the QRS complex (the onset of ventricular depolarization).
PT	preferred term
QA	quality assurance
QC	quality control
QRS	The combination of three of the graphical deflections seen on a typical electrocardiogram.
QT	Time from electrocardiogram Q wave to the end of the T wave corresponding to the electrical system
QTcB	QT corrected using Bazetts formula [$QT/(RR^{1/2})$]
RBC	red blood cell (count)
REML	restricted maximum likelihood
RR interval	intra-beat interval
SAE	serious adverse event
SAP	statistical analysis plan

Abbreviation	Term
SAS	statistical analysis software
SBP	systolic blood pressure
SD	standard deviation
SOC	system organ class
SOP	standard operating procedure
$T_{1/2}$	apparent terminal elimination half-life
TC	total cholesterol
TEAE	treatment emergent adverse event
TG	triglycerides
T_{last}	time of last measurable (positive) concentration
TLF	table, listing, figure
T_{max}	time of maximum observed plasma concentration
TR	Treatment related - includes definitely, probably, possibly, and not likely related
T-wave	repolarization of the ventricles
UGE	urine glucose excretion
ULN	upper limit of normal (value)
V_z/F	apparent volume of distribution
WBC	white blood cell (count)
WHO-DD	World Health Organization Drug Dictionary

1. INTRODUCTION

This Statistical Analysis Plan (SAP) outlines the statistical methods for the display, summary and analysis of data collected within the scope of Theracos Sub, LLC protocol version 2.0 dated 13-Jun-2017. As with any SAP, the proposed methods and approaches to the data analysis should be deemed as flexible. The analysis of the data should allow changes in the plan to the extent that deviations from the original plan would provide a more reliable and valid analysis of the data. As such, the statistical analysis to a certain degree is iterative since much of the planning is based on assumptions that require verification. The purpose of this plan is to provide general guidelines from which the analysis will proceed. Nevertheless, deviations from these guidelines must be substantiated by a sound statistical rationale.

This SAP should be read in conjunction with the study protocol and the Case Report Forms (CRFs). This version of the SAP has been developed using the final version of the protocol mentioned above and the final version of the annotated CRFs dated 26-JUL-2017 (signed 27-JUL-2017).

The SAP details the analysis of the data collected in the study and the presentation of the results of the analyses. The table, listing, and figure (TLF) shells are displayed in a companion document which provides information on the layout of the data displays.

All statistical analyses will be performed using SAS[®] version 9.4. Adverse events will be coded using the latest version of the Medical Dictionary for Regulatory Activities (MedDRA version 20.1 or newer).

This is a phase 1, single center, open-label, two-period, two-treatment, crossover study to evaluate the effect of bexagliflozin tablets, 20 mg, on the pharmacokinetics (PK) of digoxin, 0.5 mg, when co-administered in healthy subjects. Approximately 18 eligible healthy subjects will be randomized to one of the two groups (Group 1 and 2) with up to 9 subjects per group. Subjects will reside in the clinic for a total of 16 days, divided into two treatment periods, Periods 1 and 2. Subjects will be discharged and out of the clinic between the 2 treatment periods for 9 days for Group 1 and 7 days for Group 2. During the treatment periods, subjects will receive 2 treatments in differing order: Treatment A, bexagliflozin administered once daily for 8 days with digoxin co-administered on Day 3 and Treatment B, digoxin administered alone on Day 1. Safety monitoring will be conducted throughout the study.

Group 1:

Period 1, Treatment A: Subjects randomized to Group 1 will be admitted to the clinic on Day 0. Starting on Day 1, subjects will receive once daily oral dose of 20 mg bexagliflozin for 8 days; a single dose of 0.5 mg digoxin will be co-administered with bexagliflozin on Day 3. Blood samples for PK will be drawn at pre-dose and at 0.5, 1, 1.5, 2, 3, 4, 6, 8, and 12 hours (h) on Day 3, 24 h (Day 4), 48 h (Day 5), 72 h (Day 6), 96 h (Day 7), and 120 h (Day 8) after administration of digoxin. Subjects will be discharged on Day 8.

Period 2, Treatment B: Subjects will be admitted on Day 18 and receive a single oral dose of 0.5 mg digoxin on Day 19. Blood samples for PK will be drawn at pre-dose and at 0.5, 1, 1.5, 2, 3, 4, 6, 8, and 12 hours (h) on Day 19, 24 h (Day 20), 48 h (Day 21), 72 h (Day 22), 96 h (Day 23), and 120 h (Day 24) after administration of digoxin. Subjects will be discharged from the clinic on Day 24.

Group 2:

Period 1, Treatment B: Subjects randomized to Group 2 will be admitted to the clinic on Day 0. On Day 1, subjects will receive a single oral dose of 0.5 mg digoxin. Blood samples for PK will be drawn at pre-dose and at 0.5, 1, 1.5, 2, 3, 4, 6, 8, and 12 hours (h) on Day 1, 24 h (Day 2), 48 h (Day 3), 72 h (Day 4), 96 h (Day 5), and 120 h (Day 6) after administration of digoxin. Subjects will be discharged on Day 6.

Period 2, Treatment A: Subjects will be admitted on Day 14. On Day 15, subjects will start to receive once daily oral dose of 20 mg bexagliflozin for 8 days; a single dose of 0.5 mg digoxin will be co-administered with bexagliflozin on Day 17. Blood samples for PK will be drawn at pre-dose and at 0.5, 1, 1.5, 2, 3, 4, 6, 8, and 12 hours (h) on Day 17, 24 h (Day 18), 48 h (Day 19), 72 h (Day 20), 96 h (Day 21), and 120 h (Day 22) after administration of digoxin. Subjects will be discharged from the clinic on Day 22. (See Protocol Sections 3.1 to 3.3 for additional details).

2. STUDY OBJECTIVES

2.1 Primary Objective

The primary objective of this study is to evaluate the effect of bexagliflozin on the PK of digoxin after co-administration.

2.2 Secondary Objectives

The secondary objective of this study is to evaluate the safety and tolerability of digoxin when co-administered with bexagliflozin.

3. STUDY DESIGN

3.1 Study Design

This is a phase 1, single center, open-label, two-treatment period, crossover study to evaluate the effect of bexagliflozin tablets, 20 mg, on the PK of digoxin, 0.5 mg after co-administration in healthy subjects. Approximately 18 eligible healthy subjects who consent to the study will be enrolled into the study and randomized to one of the two groups with up to 9 subjects per group. Each subject will participate in 2 periods during which subjects will receive 2 treatments (Treatment A: bexagliflozin co-administered with digoxin, Treatment B: digoxin alone). During the duration of the study, each subject will receive 8 single doses of bexagliflozin and 2 single doses of digoxin.

Group 1

Approximately 9 subjects will be admitted to the clinic on Day 0 and will receive the following study drugs in two treatment periods:

Period 1, Treatment A

Subjects will receive a single oral dose of 20 mg bexagliflozin tablet daily starting on Day 1 for 8 days, and a single oral dose of 0.5 mg digoxin will be co-administered with bexagliflozin on Day 3. Blood samples for PK will be drawn at pre-dose and at 0.5, 1, 1.5, 2, 3, 4, 6, 8, and 12 hours (h) on Day 3, 24 h (Day 4), 48 h (Day 5), 72 h (Day 6), 96 h (Day 7), and 120 h (Day 8) after administration of digoxin. Subjects will be discharged on Day 8 after all study activities are completed.

Period 2, Treatment B

Subjects will be admitted on Day 18. On Day 19, subjects will receive a single oral dose of 0.5 mg digoxin. Blood samples for PK will be drawn at pre-dose and at 0.5, 1, 1.5, 2, 3, 4, 6, 8, and 12 hours (h) on Day 19, 24 h (Day 20), 48 h (Day 21), 72 h (Day 22), 96 h (Day 23), and 120 h (Day 24) after administration of digoxin. Subjects will be discharged on Day 24 after all study activities are completed.

Group 2

Approximately 9 subjects will be admitted to the clinic on Day 0 and will receive the following study drugs in two treatment periods:

Period 1, Treatment B

Subjects will receive a single oral dose of 0.5 mg digoxin on Day 1. Blood samples for PK will be drawn at pre-dose and at 0.5, 1, 1.5, 2, 3, 4, 6, 8, and 12 hours (h) on Day 1, 24 h (Day 2), 48 h (Day 3), 72 h (Day 4), 96 h (Day 5), and 120 h (Day 6) after administration of digoxin.

Period 2, Treatment A

Subjects will be admitted on Day 14. Subjects will receive a single oral dose of 20 mg bexagliflozin daily for 8 days starting on Day 15, and a single oral dose of 0.5 mg digoxin will be co-administered with bexagliflozin on Day 17. Blood samples for PK will be drawn at pre-dose and at 0.5, 1, 1.5, 2, 3, 4, 6, 8, and 12 hours (h) on Day 17, 24 h (Day 18), 48 h (Day 19), 72 h (Day 20), 96 h (Day 21), and 120 h (Day 22) after administration of digoxin. Subjects will be discharged on Day 22 after all study activities are completed.

Clinical laboratory tests and safety monitoring will be conducted during both treatment periods for both groups.

3.2 Randomization

A total of 18 healthy subjects will be enrolled and randomly assigned to group 1 or group 2 in a 1:1 ratio. Subjects who discontinue the study after randomization will not be replaced.

3.3 Hypothesis Testing

No formal statistical hypothesis testing will be conducted for this study.

3.4 Interim Analysis

There will be no interim analysis conducted.

3.5 Sample Size

The sample size for this study is not based upon formal statistical consideration. The sample size is considered adequate to characterize the PK of digoxin, to assess potential drug-drug interactions and to provide safety and tolerability data on the compound when administered either alone or with bexagliflozin.

Table 1. Schedule of Events – Group 1

Evaluation	Screening	Period 1: Treatment A										Period 2: Treatment B				
		0	1	2	3	4	5	6	7	8	18	19	20	21	22	
Days to randomization (days)	-21 to -1															
Medical history and ICF	X															
Demographics	X															
Review for I/E criteria ¹	X		X													
Physical exam ²	X	X			X						X	X				
Admission or discharge ³		X								X	X					
Randomization			X													
Administer bexagliflozin ⁴			X	X	X	X	X	X	X	X						
Administer digoxin ⁴					X							X				
Vital signs ⁵	X		X		X					X		X				
ECG ⁶	X		X		X	X						X	X			
Urinalysis ⁷	X		X		X					X		X				
Urine drug screening	X															
Urine pregnancy test (for females only)	X	X									X					
Blood draw for clinical lab tests ⁸	X	X			X					X		X				
Blood samples for PK ⁹					X	X	X	X	X	X		X	X	X	X	X
Adverse event and concomitant medication		X	X	X	X	X	X	X	X	X	X	X	X	X	X	X
Study termination																

Screening criteria must be re-confirmed on Day 1 prior to randomization, based on results for clinical lab tests from Day 0 and vital signs, ECG and urinalysis results.

Height and weight will be recorded as part of the physical examination. Height will be recorded once at screening only. A complete physical exam (PE) will be performed at screening, Day 1, Day 3, Day 18, and Day 24. A partial PE will be performed on Days 0, 3, 18 and 19. On Days 3 and 19, the PE will be performed prior to randomization. All subjects will be admitted to the clinic on Day 0, discharged on Day 8 for Period 1. For Period 2, subjects will be admitted on Day 18 and discharged on Day 22 for dosing schedule.

Vital signs will include pulse, body temperature, respiratory rate, and blood pressure after at least 5 minutes of rest. On Days 1, 3, and 19, vital signs will be measured prior to randomization. Vital signs will also be measured on Day 8 and Day 24.

ECG will be conducted after 5 min of rest. On Day 1, ECG will be recorded pre-dose and 4 hr post-dose of bexagliflozin. On Days 3, and 19, ECG will be recorded pre-dose and post-dose of digoxin at hours 4 and 8. On Days 4 and 20 ECG will be recorded at 24 hrs post dose of digoxin on Day 3 and Day 19 respectively. ECG will be recorded at additional time points when clinically indicated.

Urine will be collected for urinalysis on indicated days or if symptoms or signs suggestive of urinary tract infection are present. If urine is dipstick positive, a sample is to be sent for microscopic evaluation and culture. Urinalysis on Days 1, 3, and 19 will be done pre-dose.

Clinical chemistry and hematology will be drawn after a minimum of 10 h fasting prior to breakfast. Infectious disease testing will be conducted at screening. A test blood draw will be done pre-dose.

Blood samples will be collected at the following time points: pre-dose of digoxin (0 h) and 0.5, 1, 1.5, 2, 3, 4, 6, 8, 12, 24, 48, 72, 96, and 120 h post dose of digoxin.

Table 2. Schedule of Events – Group 2

Evaluation	Screening	Period 1: Treatment B										Period 2: Treatment A						
		0	1	2	3	4	5	6	14	15	16	17	18	19	20	21	22	
Days to randomization (days)	-21 to -1																	
Medical history and ICF	X																	
Demographics	X																	
Review for I/E criteria ¹	X		X															
Physical exam ²	X	X	X						X			X						X
Admission or discharge ³		X							X	X								X
Randomization			X															
Administer bexagliflozin ⁴											X	X	X	X	X	X	X	X
Administer digoxin ⁴			X									X						
Vital signs ⁵	X		X						X		X		X					X

ECG ⁶	X		X	X					X		X	X				X
Urinalysis ⁷	X		X					X	X		X					X
Urine drug screening	X															
Urine pregnancy test (for females only)	X	X						X								
Blood draw for clinical lab tests ⁸	X	X						X	X		X					X
Blood samples for PK ⁹			X	X	X	X	X	X				X	X	X	X	X
Adverse event and concomitant medication		X	X	X	X	X	X	X	X	X	X	X	X	X	X	X
Study termination																X

- ¹ Eligibility criteria will be re-confirmed on Day 1 prior to randomization, based on results for clinical lab tests from Day 0 and vital signs, ECG and urinalysis results from Day 1 pre-dose.
- ² Weight and height will be recorded as part of the physical examination. Height will be recorded once at screening only. A complete physical exam (PE) will be performed at screening visit and the day of study termination, Day 22. A partial PE will be performed on Days 0, 1, 14, and 17. On Days 1 and 17, the PE will be performed prior to dosing.
- ³ Group 2 subjects will be admitted to the clinic on Day 0, discharged on Day 6 for Period 1. For Period 2, subjects will be admitted on Day 14 and discharged on Day 22.
- ⁴ See Appendix 2 for dosing schedule.
- ⁵ Vital signs include pulse, body temperature, respiratory rate, and blood pressure after at least 5 minutes of rest. On Days 1, 15, and 17, vital signs will be measured pre-dose and 4 hr post-dose. Vital signs will also be measured on Day 6 and Day 22.
- ⁶ 12-lead ECG will be conducted after 5 min of rest. On Day 15, ECG will be recorded pre-dose and 4 hr post-dose of bexagliflozin. On Days 1 and 17, ECG will be recorded at pre-dose and post-dose of digoxin at hours 4, 8. On Days 2 and 18 ECG will be recorded at 24 hrs post dose of digoxin on Day 1 and Day 17 respectively. ECG will also be recorded on Day 22. ECG will be recorded at additional time points when clinically indicated.
- ⁷ Clean-catch urine will be collected for urinalysis on the indicated days, or if symptoms or signs suggestive of urinary tract infection are present. If urine is dipstick positive for WBC or blood, sample is to be sent for microscopic evaluation and culture. Urinalysis on Days 1, 15 and 17 will be done pre-dose.
- ⁸ Blood for clinical chemistry and hematology will be drawn after a minimum of 10 h fasting prior to breakfast. Infectious disease testing will be conducted at screening only. Clinical lab test blood draw will be done pre-dose.
- ⁹ PK plasma samples will be collected at the following time points: pre-dose of digoxin (0 h) and 0.5, 1, 1.5, 2, 3, 4, 6, 8, 12, 24, 48, 72, 96, and 120 h post dose of digoxin.

4. DATA AND ANALYTICAL QUALITY ASSURANCE

The overall quality assurance (QA) procedures for the study data, statistical programming and analyses are described in Everest’s Standard Operating Procedures (SOPs). Detailed data management (DM) procedures are documented in the Data Management Plan, Data Validation Check Specifications, and Data Review Plan. Detailed statistical and programming quality control (QC) and QA procedures are documented in the Statistical Analysis and Programming QC/QA Plan.

The study endpoints and analytic approaches are both prospectively defined and documented in the protocol and in this SAP. The SAP will be finalized, and protocol violations will be identified and decisions for inclusion and exclusion of subjects from the PK Population will be made prior to the database lock and data analysis.

5. ANALYSIS POPULATIONS

Two subject populations will be evaluated during this study and are defined as follows:

5.1 Safety Population

The Safety Population will include all randomized subjects who receive at least one dose of either study drug. Subjects will be analyzed according to the treatment received.

5.2 Pharmacokinetic Population

The PK Population will include all randomized subjects who receive at least one dose of study drug and who have sufficient plasma digoxin measurements to derive at least one PK parameter following dosing.

The PK Population will be used to summarize the PK parameters. Subjects will be analyzed according to the treatment received.

6. SPECIFICATION OF ENDPOINTS AND VARIABLES

6.1 Demographic and Baseline Characteristics

Demographic variables consist of the following:

- Age in years (continuous) derived as the integer value of (informed consent date – date of birth + 1)/365.25
- Sex
- Race
- Ethnicity

Baseline characteristics consist of the following:

- Body mass index (BMI)
- Weight (kg)
- Height (cm)
- Vital signs
 - systolic blood pressure (SBP, mmHg)
 - diastolic blood pressure (DBP, mmHg)
 - oral temperature (°C)
 - pulse (beats per minute)
 - respiration rate
- Electrocardiogram (ECG) parameters
 - RR interval (msec)
 - PR interval (msec)
 - QRS duration (msec)
 - QT interval (msec)
 - QTcB interval (msec)
- Medical history and baseline conditions
- Clinical laboratory tests
- Prior and concomitant medication
- Physical examination

6.1.1 Study Day and Visit Window Definitions

Table 3. Time Windows for Safety Assessments

Time Windows for Safety Assessments			
Scheduled Visit Number	Visit (label)	Time Interval (day)	Target Time Point (day)
1	Screening	-21 to -1	-21 to -1

2	Day 0	0	0
3	Day 1	1	1
4	Day 2	2	2
5	Day 3	3	3
6	Day 4	4	4
7	Day 5	5	5
8	Day 6	6	6
9	Day 7	7	7
10	Day 8	8	8
11	Day 14	14	14
12	Day 15	15	15
13	Day 16	16	16
14	Day 17	17	17
15	Day 18	18	18
16	Day 19	19	19
17	Day 20	20	20
18	Day 21	21	21
19	Day 22	22	22
20	Day 23	23	23
21	Day 24	24	24

Data obtained during unscheduled visits will be allocated to the scheduled visit corresponding to the visit window they fall in as specified in Section 6.1.1. Safety data obtained during unscheduled time points will be allocated to the scheduled time point corresponding to the time window in which they fall. Data will be analyzed based on the nominal visits and nominal time points. If the data from the nominal visit or time point is missing, data from unscheduled visits for the same nominal visit or time point will be used. If multiple unscheduled assessments fall in the same visit window or time point, the non-missing assessment closest to target time point will be selected for analysis.

For ECG safety data the below data handling rules will apply:

For ECG tests that occur after pre-dose but prior to 4 hrs post-dose, these results will be associated with the 4 hr post-dose assessment. For ECG tests that occur after 4 hrs post dose, but within a 2 hour window of the 4 hour postdose timepoint this data will be associated with the 4 hr post-dose timepoint.

For ECG tests that occur after the 4 hr post-dose timepoint but prior to 8 hrs post-dose, these results will be associated with the 8 hr post-dose assessment if they occur within 2 hrs prior to the 8 hr post-dose timepoint.

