6.5 Electrocardiography

A 12-lead electrocardiography (ECG) will be conducted as listed in [Appendix 1](#) and whenever clinically indicated.

This procedure should be performed in the supine position after at least 5 minutes of rest. ECG parameters measured will be the RR interval, PR interval, QRS duration, and QT. Each ECG should also be assessed by the investigator for signs of ischemia, clinically significant hypertrophy, and clinically significant T-wave abnormalities.

It is the investigator or designee's responsibility to review the results of the ECG as they become available. For each abnormal ECG result, the investigator needs to ascertain if this is a clinically significant change from the screening ECG for that individual subject. This determination, however, does not necessarily need to be made the first time an abnormal result is observed. The investigator may repeat the ECG to verify the results of the original result. If the ECG result is determined to be a clinically significant and an abnormal change from baseline for that subject, this is considered an AE.

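### The SAP's ECG hour windows are lopsided: if a scheduled 4 h or 8 h ECG is missing, a badly timed unscheduled tracing can replace it while a better-timed one cannot

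*SAP*

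**What the plan says.** SAP 6.1.1 has two layers. The general rules come first. Scheduled data follow the nominal schedule: "Data will be analyzed based on the nominal visits and nominal time points". Unscheduled safety data are placed in the time point whose window they fall in, and they serve only as a fallback: when the nominal value is missing, "data from unscheduled visits for the same nominal visit or time point will be used". If several unscheduled assessments share a window, the one nearest the target is taken. SAP Table 3 gives windows in whole days only.

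Three ECG rules follow, and they are the only windows expressed in hours:

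- Before 4 h: "For ECG tests that occur after pre-dose but prior to 4 hrs post-dose, these results will be associated with the 4 hr post-dose assessment".
- After 4 h, if "within a 2 hour window of the 4 hour postdose timepoint this data will be associated with the 4 hr post-dose timepoint".
- Before 8 h: "these results will be associated with the 8 hr post-dose assessment if they occur within 2 hrs prior to the 8 hr post-dose timepoint".

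On digoxin days the schedule has ECGs pre-dose and at 4 h and 8 h. The 24 h ECG falls on the next study day (Days 4 and 20 in Group 1, Days 2 and 18 in Group 2). Day 1 in Group 1 and Day 15 in Group 2 have a 4 h ECG after bexagliflozin, with no digoxin that day and no 8 h ECG. SAP 8.4.4 summarises ECG changes from baseline descriptively, by treatment and treatment group, and lists all ECG results for the Safety Population.

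**The concern.** A substitution window should admit tracings close to the target and reject distant ones. These do not. The 4 h window stretches back to the moment of dosing but only 2 h forward. The 8 h window reaches 2 h back and not at all forward. The preference for the nearest assessment cannot repair this, because it chooses only among tracings already in the same window.

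The safety and tolerability of digoxin given with bexagliflozin is the secondary objective, and ECG is one of the listed safety variables. Both documents allow extra ECGs when clinically indicated, so off-schedule tracings may exist, and some may be prompted by symptoms. If the scheduled ECG is missing, such a tracing taken soon after dosing could enter the 4 h mean change, while a tracing shortly after 8 h could not supply the 8 h value.

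**Working it through.** No sample-size or error-rate figure is involved, so the check applies the rules as written to ECG times after dosing (t, in hours).

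**Inputs, all from SAP 6.1.1**

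- Rule 1: 0 < t < 4 goes to 4 h.
- Rule 2: t > 4 and within the 2 h window goes to 4 h. The text does not say whether this means up to 2 h later or a total width of 2 h (±1 h), nor whether the limit is included.
- Rule 3: 6 to < 8 goes to 8 h. Inclusion of 6 h is not stated.

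**Allocation under three readings**

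| ECG time (h:min) | Up to +2 h, limits included | Up to +2 h, limits excluded | ±1 h |
|---|---|---|---|
| 0:03, 0:30, 1:00, 2:00, 3:54 | 4 h | 4 h | 4 h |
| 5:00 | 4 h | 4 h | 4 h |
| 5:30, 5:59 | 4 h | 4 h | none |
| 6:00 | both | none | 8 h |
| 6:01, 7:00, 7:57 | 8 h | 8 h | 8 h |
| 8:03, 8:30, 9:00, 10:00, 12:00 | none | none | none |

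Exactly 4:00 and 8:00 also match no rule. That is harmless if the rules concern off-schedule tracings only.

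**Asymmetry around each target, first reading**

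- 4 h slot: on a one-minute grid the earliest eligible time is 0:01, so the greatest early error is 4:00 − 0:01 = 3 h 59 min. The greatest late error is 6:00 − 4:00 = 2 h.
- 8 h slot: the greatest early error is 8:00 − 6:00 = 2 h. No late time is eligible.

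**Worked case.** The scheduled 8 h ECG is missing, and unscheduled ECGs exist at 6 h 05 min and 8 h 10 min. Their distances from target are 8:00 − 6:05 = 115 min and 8:10 − 8:00 = 10 min. Only the first lies in the 8 h window, so it is used.

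**Length of the late gap.** The protocol has digoxin taken in the morning but gives no clock time. Assuming dosing between 07:00 and 10:00, 8 h post-dose falls between 15:00 and 18:00. That leaves 24 − 15 = 9 h down to 24 − 18 = 6 h before midnight, when the next study day's window in Table 3 takes over. An unscheduled ECG in that stretch belongs to the dosing-day visit but to no post-dose time point.

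**When it reaches a summary.** Two conditions must hold: the scheduled 4 h or 8 h ECG is missing, and no closer eligible unscheduled ECG exists. With about 18 subjects per treatment, a substitute that differs from the on-time value by d shifts that mean by d/18. If the table is also split by treatment group (up to 9 subjects), the shift is d/9.

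**The case against.** The strongest reply is that the nominal-time sentence governs and the trigger is narrow. Subjects are resident in the clinic on these days, so missing scheduled ECGs should be few. Even then, SAP 8.4.4 lists every ECG result, and Protocol 6.5 makes a clinically significant abnormal change an adverse event. No tracing disappears from the report; at most it is left out of a descriptive mean. The SAP plans no formal hypothesis testing. Assigning any early post-dose ECG to the first post-dose assessment may also have been deliberate. All of this stands as a limit on size, but none of it explains why the 8 h slot has no late side or who owns 6 h.

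A reader might infer more than the documents support:

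- *That every ECG after 8 h is lost.* A scheduled 8 h ECG taken a few minutes late keeps its nominal slot. The 24 h ECG is scheduled on the next study day, which has its own visit window in Table 3.
- *That about half of the scheduled 8 h ECGs would be unallocated.* This needs the ECG rules to override the nominal-time sentence, which no text says. The same reading would leave ECGs at exactly 4:00 and 8:00 without a slot, so it is implausible. It also assumes that actual times fall evenly around 8 h, for which the documents give no basis.
- *That ECGs around 6 h are double-counted.* Both rules are met only at exactly 6:00, and only if both limits are included.
- *That verification repeats feed the problem.* Protocol 6.5 says "The investigator may repeat the ECG to verify the results of the original result". Such a repeat presupposes an original result, so the nominal value is present and no substitution occurs. The relevant tracings are other unscheduled ECGs, such as clinically indicated ones.

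**Conclusion.** The point holds as a minor defect in a stated rule. For unscheduled ECGs that replace a missing scheduled one, the 4 h slot runs from just after dosing to 6 h, and the 8 h slot runs from 6 h to before 8 h. The 6 h boundary is unassigned, and unscheduled ECGs after 8 h on the dosing day have no time point. The rules can therefore select a worse tracing over a better one, as the 6 h 05 min against 8 h 10 min case shows.

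The size is small: probably few affected values, each with about 1/18 of the weight of a treatment mean, in descriptive ECG safety summaries only. The PK analysis is not touched.

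This rests on three assumptions: nominal time takes precedence for scheduled ECGs, the 2 h window after 4 h means up to 2 h later, and about 18 subjects contribute per treatment. Under the ±1 h reading, unscheduled ECGs after 5 h and before 6 h would also have no slot. The missing lower limit at 4 h and the missing late side at 8 h are the same on every reading.

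**What to change.** Replace the three ECG rules in SAP 6.1.1 with non-overlapping two-sided windows measured from that day's study-drug dose. For example:

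- 4 h slot: 2 h to < 6 h, on days with a 4 h ECG.
- 8 h slot: 6 h to 10 h, on days with an 8 h ECG.
- 24 h ECG: left to its day visit window in Table 3.
- ECGs outside every window: listed only.

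These limits extend the SAP's own 2 h figure to both sides; the outer limits are a proposal and do not come from the documents. Anchoring to that day's dose matters because windows measured from digoxin would leave out the 4 h post-bexagliflozin ECGs on Day 1 (Group 1) and Day 15 (Group 2).

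Add one sentence saying that the windows apply only to unscheduled ECGs, and only when the nominal one is missing. That settles precedence. In the worked case both tracings would then fall in the 8 h window, and the existing nearest-to-target rule would choose the one at 8 h 10 min.

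The cost is a few lines of SAP text and a small programming change, with no new data. The drawback is that an ECG before 2 h no longer fills a missing 4 h cell, so that cell may stay missing.
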